3.3.2 Exclusion Criteria

Subjects will be ineligible for this study if they meet **any** of the following criteria:

All Parts:

1. Prior malignancy, except for adequately treated basal cell or squamous cell skin cancer, in situ cervical cancer, or other cancer from which the subject has been

Protocol: ACE-LY-001

disease free for ≥2 years or which will not limit survival to <2 years. Note: These cases must be discussed with the medical monitor.

- 2. A life-threatening illness, medical condition, or organ system dysfunction which, in the investigator's opinion, could compromise the subject's safety, interfere with the absorption or metabolism of acalabrutinib and/or ACP-319, or put the study outcomes at undue risk.
- 3. Significant cardiovascular disease such as uncontrolled or symptomatic arrhythmias, congestive heart failure, or myocardial infarction within 6 months of screening, or any Class 3 or 4 cardiac disease as defined by the New York Heart Association Functional Classification.
- 4. Malabsorption syndrome, disease significantly affecting gastrointestinal (GI) function, resection of the stomach, extensive small bowel resection that is likely to affect absorption, symptomatic inflammatory bowel disease, partial or complete bowel obstruction, or gastric restrictions and bariatric surgery such as gastric bypass.
- 5. CNS involvement by lymphoma/leukemia.
- 6. Any therapeutic antibody within 4 weeks of first dose of study drug.
- 7. The time from the last dose of the most recent chemotherapy or experimental therapy to the first dose of study drug is <5 times the half-life of the previously administered agent(s).
- Any prior therapy with BTK, PI3Kδ, or SYK inhibitors or BCL-2 inhibitors
 (e.g., venetoclax/ABT-199). Note: Prior treatment with reversible, noncovalent BTK
 inhibitors is not excluded on this protocol.
- 9. Ongoing immunosuppressive therapy, including systemic or enteric corticosteroids for treatment of lymphoid cancer or other conditions. Note: Subjects may use topical or inhaled corticosteroids or low-dose steroids (≤10 mg of prednisone or equivalent per day) as therapy for comorbid conditions. During study participation, subjects may also receive systemic or enteric corticosteroids as needed for treatment-emergent comorbid conditions.
- 10. Use of a strong inhibitor or inducer of cytochrome P450 (CYP)3A (see Appendix 3) within 7 days before dose of study drug or expected requirement for use of a CYP3A inhibitor or inducer during the first 28 days of administration of study drugs.
- 11. Remains not applicable for this amendment.
- 12. Known history of HIV, serologic status reflecting active hepatitis B or C infection, or any uncontrolled active systemic infection.

Protocol: ACE-LY-001

 a) Subjects who are hepatitis B core antibody (anti-HBc) positive and who are surface antigen negative will need to have a negative polymerase chain reaction (PCR) result before enrollment. Those who are hepatitis B surface antigen (HbsAg) positive or hepatitis B PCR positive will be excluded.

- b) Subjects who are hepatitis C antibody positive will need to have a negative PCR result before enrollment. Those who are hepatitis C PCR positive will be excluded.
- 13. Major surgery within 4 weeks before first dose of study drugs. Note: If a subject had major surgery, they must have recovered adequately from any toxicity and/or complications from the intervention before the first dose of study drug.
- 14. History of stroke or intracranial hemorrhage within 6 months before the first dose of study drugs.
- 15. Ongoing, drug-induced liver injury, alcoholic liver disease, nonalcoholic steatohepatitis, primary biliary cirrhosis, ongoing extrahepatic obstruction caused by cholelithiasis, cirrhosis of the liver, or portal hypertension.
- 16. History of or ongoing drug-induced pneumonitis.
- 17. Part 2 only: ANC <0.5 x 10⁹/L or platelet count <50 x 10⁹/L unless due to disease involvement in the bone marrow.
- 18. Estimated creatinine clearance of <30 mL/min, calculated using the formula of Cockcroft and Gault [(140-Age) Mass (kg)/(72 creatinine mg/dL); multiply by 0.85 if female].
- 19. Significant screening ECG abnormalities including left bundle-branch block, second-degree AV block type II, third-degree AV block, Grade ≥2 bradycardia, and QTc >480 msec.
- 20. Breastfeeding or pregnant.
- 21. Concurrent participation in another therapeutic clinical trial.
- 22. History of bleeding diathesis (e.g., hemophilia or von Willebrand disease).
- 23. Requires or receiving anticoagulation with warfarin or equivalent vitamin K antagonists (e.g., phenprocoumon) within 7 days of first dose of study drug.
- 24. Requires treatment with proton-pump inhibitors (e.g., omeprazole, esomeprazole, lansoprazole, dexlansoprazole, rabeprazole, or pantoprazole). Subjects receiving proton-pump inhibitors who switch to H2-receptor antagonists or antacids are eligible for enrollment to this study.
- 25. Total bilirubin >1.5 x upper limit of normal (ULN), or aspartate aminotransferase (AST) or alanine aminotransferase (ALT) >3.0 x ULN.
- 26. Serum amylase >1.5 x ULN or serum lipase >1.5 x ULN.

Protocol: ACE-LY-001

27. Presence of a GI ulcer diagnosed by endoscopy within 3 months before screening.

- 28. Concomitant use of medicines known to cause QT prolongation or Torsades de pointes within 7 days of starting study drug (see Appendix 2).
- 29. Active cytomegalovirus (CMV) infection (positive CMV immunoglobulin [Ig] M and/or positive PCR result).

3.3.3 Replacement of Subjects

Any subject who does not complete study therapy through Cycle 2 for reasons other than the occurrence of a Cycle 1 DLT in Part 1 may be replaced at the discretion of the study investigators and sponsor. Should the decision be made to replace a subject, the replacement subject will be assigned to the same treatment cohort as the original subject.

3.3.4 Enrollment Procedures

Enrollment of a subject into the study will be performed according to the following procedure:

The study center will notify the sponsor when a clinically eligible subject is identified and is ready to screen, to ensure enrollment availability on the study.

After the subject has signed and dated the ICF and all screening procedures have been completed, the site must submit the completed Enrollment Confirmation Form and supporting documents as required in the Enrollment Confirmation Form to the sponsor for review and approval before enrollment.

After subject eligibility has been reviewed and confirmed by the medical monitor, the subject can be officially enrolled into the study. The sponsor will aim to fax/email a completed Enrollment Confirmation Form with the cohort allocation information to the study center within 24 hours after receiving all required documentation. The enrollment date will be the date that the sponsor confirms enrollment.

Treatment must begin within 21 days of the start of the screening visit after the site has received the cohort allocation from the sponsor.

3.4 STUDY DRUGS

3.4.1 Premedications

No specific premedications or supporting medications are required in conjunction with acalabrutinib or ACP-319 administration.

Tumor lysis syndrome has not been observed, to date, with either acalabrutinib or ACP-319. Whether there could be an increased likelihood of tumor lysis syndrome when coadministering acalabrutinib and ACP-319 is unknown. Investigators are at liberty to

Protocol: ACE-LY-001

consider additional monitoring and prophylaxis for tumor lysis syndrome according to local practices (see Section 3.10).

As general precautions considering the subject population, institution of antibiotic prophylaxis for *Pneumocystis (carinii) jiroveci* and use of intravenous immunoglobulin (IVIG) may be considered in selected study subjects (see Section 3.10).

3.4.2 Formulation, Packaging, and Storage

Acalabrutinib and ACP-319 are manufactured according to current Good Manufacturing Practice regulations and will be provided to the investigational site by Acerta Pharma or designee. They should be stored according to the instructions on the label that is affixed to the package containing each respective drug product. Both drug products are provided as capsules intended for oral administration.

Acalabrutinib will be provided in white, high-density polyethylene bottles.

ACP-319 will be provided in high-density polyethylene bottles.

If a drug shipment arrives damaged, or if there are any other drug complaints, a Product Complaint Form should be completed and emailed or faxed to the sponsor or the sponsor's representative. Refer to the acalabrutinib Investigator Brochure for additional information.

CCI

3.4.3 Administration of Study Drug

Investigators are prohibited from supplying acalabrutinib or ACP-319 to any subjects not properly enrolled in this study. The investigator must ensure that subjects receive acalabrutinib or ACP-319 only from personnel who fully understand the procedures for administering the drug.

Both drugs are intended to be administered orally BID with 8 ounces (approximately 240 mL) of water. Subjects receiving acalabrutinib (and previously ACP-319) combination therapy should be instructed to take each dose of both study drugs at the same time on an empty stomach, defined as no food 2 hours before and 1 hour after dosing. Subjects receiving acalabrutinib monotherapy are not required to fast before and after acalabrutinib administration. The capsules should be swallowed intact. Subjects should not attempt to open the capsules or dissolve them in water. Doses should be taken 12 hours (± 60 minutes) apart.

Protocol: ACE-LY-001

If a dose is not taken within the allowed window, it can be taken up to 3 hours after the scheduled time with a return to the normal schedule the same or the following day. If the delay is >3 hours, the dose should not be taken, and the subject should take the next dose at the next scheduled time.

Guidance on coadministration of acalabrutinib with agents that affect gastric pH is provided in Section 3.11.3.

3.4.4 Assuring Subject Compliance

Subjects will receive their morning dose in the clinic on Cycle 1 Days 1, 8, 15, 22, and 28, Cycle 2 Days 15 and 28, and Cycles 3 and 4 Day 28. For treatments that are taken in the clinic, subjects should take the dose from the drug dispensed for them for that particular time period. All other treatments will be taken at home. Subjects will receive a drug diary to record the specific time each dose was taken and to record reasons for any missed doses.

Subject compliance will be assessed at every visit. The subject will be instructed to bring the diary and any remaining capsules to the clinic at their next visit. The study staff will review the diary and ask the subject if all of the capsules were administered. Any remaining or returned capsules will be counted and recorded as described in Section 7.7. Returned capsules must not be re-dispensed to another subject.

3.5 STUDY DRUG DOSING

Regimens:

Part 1:

The acalabrutinib dose will be fixed at 100 mg BID. The ACP-319 dose will be escalated as follows:

Cohort 1: Acalabrutinib 100 mg BID + ACP-319 25 mg BID continuously

Cohort 2: Acalabrutinib 100 mg BID + ACP-319 50 mg BID continuously

Cohort 3: Acalabrutinib 100 mg BID + ACP-319 100 mg BID continuously

Twenty-eight days of study drug administration is defined as 1 cycle. Each dosing cohort will be enrolled sequentially with 6 subjects per cohort. If ≤1 DLT (see Section 3.7 for definition) is observed in the cohort during Cycle 1, escalation to the next cohort will proceed. If ≥2 DLTs are observed during Cycle 1, dosing at that dose and higher will be suspended and the MTD will be established as the previous cohort. The MTD is defined as the largest daily dose for which fewer than 33% of the subjects

Protocol: ACE-LY-001

experience a DLT during Cycle 1. Escalation will end with Cohort 3 or sooner if the MTD is reached in an earlier cohort.

Note: Under Amendment 3 of this protocol, subjects with CLL/SLL will receive acalabrutinib monotherapy (100 mg BID).

Part 2:

Acalabrutinib 100 mg BID and ACP-319 50 mg BID continuously.

Note: Under Amendment 3 of this protocol, subjects with CLL/SLL will receive acalabrutinib monotherapy (100 mg BID).

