Regimens: Part 1: Cohort 1: Acalabrutinib 100 mg BID + ACP-319 25 mg BID continuously Cohort 2: Acalabrutinib 100 mg BID + ACP-319 50 mg BID continuously Cohort 3: Acalabrutinib 100 mg BID + ACP-319 100 mg BID continuously Part 2: Acalabrutinib 100 mg BID + ACP-319 50 mg BID continuously Note: Under Amendment 6 of this protocol, all active subjects will receive acalabrutinib monotherapy (100 mg BID). Concomitant The effect of agents that reduce gastric acidity (antacids or Medications: proton-pump inhibitors) on acalabrutinib absorption was evaluated in a healthy volunteer study (ACE-HV-004). Results from this study indicate that subjects should avoid the use of calcium carbonate-containing drugs or supplements for a period of at least 2 hours before and at least 2 hours after taking acalabrutinib. Use of omeprazole, esomeprazole, lansoprazole, or any other proton-pump inhibitors while taking acalabrutinib is not recommended due to a potential decrease in study drug exposure. However, the decision to treat with proton-pump inhibitors during the study is at the investigator's discretion, with an understanding of the potential benefit to the subject's GI condition and a potential risk of decreased exposure to acalabrutinib. Although the effect of H2-receptor antagonists (such as famotidine or ranitidine) on acalabrutinib absorption has not been evaluated, if treatment with an H2-receptor antagonist is required, the H2-receptor antagonist should be taken approximately 2 hours after an acalabrutinib dose. The concomitant use of strong inhibitors/inducers of CYP3A with acalabrutinib should be avoided when possible. If a subject requires short-term treatment with a strong CYP3A inhibitor (such as anti-infectives for up to 7 days), interrupt acalabrutinib treatment. Detailed information on concomitant administration of drugs that inhibit or induce CYP3A is provided in Section 3.11.3 and Appendix 3. Statistics: Descriptive statistics (including means, standard deviations, and medians for continuous variables and proportions and confidence intervals [CIs] for discrete variables) will be used to summarize data as appropriate. As appropriate, analyses will be performed by dosing cohort, cancer type, or overall. Depending on dose escalation into subsequent cohorts and

Protocol: ACE-LY-001

potential expansion cohorts, up to 108 evaluable subjects will be enrolled in this study.

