MCL, characterized by documentation of monoclonal B cells that have a chromosome translocation t(11;14)(q13;q32) and/or overexpress cyclin D1 iNHL

- FL, Grade 1, 2, or 3a
- o WM
- o CLL/SLL

Multiple myeloma (MM)

B-cell acute lymphoblastic leukemia (B-ALL)

Note: Under Amendment 4 of this protocol, enrollment in Part 2 is closed for all cohorts except the non-GCB DLBCL cohort.

Note: Under Amendment 6 of this protocol, all active subjects will receive acalabrutinib monotherapy (100 mg BID).

Treatment with acalabrutinib (and previously ACP-319), in Part 1 and Part 2, may be continued until disease progression or an unacceptable drug-related toxicity occurs as defined in the protocol. Dose modification provisions are provided in the study protocol. Note: Temporary withholding of study drug for as little as 7 days can cause a transient worsening of disease and/or of constitutional symptoms. Refer to Section 3.12 for more information on assessing disease progression under these circumstances. All subjects who discontinue study treatment will have a safety follow-up (SFU) visit 30 (+ 7) days after the last dose of study drug and will be followed every 3 months thereafter until disease progression or the start of alternative anticancer treatment.

All subjects will have hematology, chemistry, and urinalysis safety panels performed at screening. Once dosing commences (Day 1), all subjects receiving acalabrutinib (and previously ACP-319) combination therapy will be evaluated for safety, including serum chemistry and hematology, on Cycle 1 Days 1, 8, 15, 22, and 28, Cycle 2 Days 15 and 28, then monthly through Cycle 24, and every 3 months thereafter. ECGs will be obtained at screening, repeatedly during Cycle 1, at each study visit through Cycle 6, and at each study visit in Cycles 9 and 12. PK testing will be done in Cycles 1 to 4. PD testing will be done in Cycles 1 and 2, and at the treatment termination (TT) visit. Radiologic tumor assessments will be done at screening and at the end of Cycle 2, Cycle 4, and Cycle 6; every 3 cycles (12 weeks) through Cycle 18, and then every 6 cycles thereafter, or more frequently at the investigator's discretion.

[figure not shown]
Protocol: ACE-LY-001

Refer to Appendix 5 for a comprehensive list of study assessments and their timing (acalabrutinib monotherapy).

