3.8 DOSING DELAYS AND MODIFICATIONS

Subjects should be followed closely for AEs or laboratory abnormalities that might indicate acalabrutinib- or ACP-319-related toxicity. If a subject experiences a treatment-related DLT or other AE requiring dose modification during the course of

Protocol: ACE-LY-001

therapy, then acalabrutinib, ACP-319, or both drugs should be held, as necessary, until the AE resolves or stabilizes to an acceptable degree.

When restarting treatment, study drugs should be re-introduced in a staggered fashion, after discussion with the medical monitor. If both drugs were withheld, acalabrutinib (at the original or modified dose) should be given alone for at least 7 days, and the subject monitored closely for recurrence of AEs, before adding ACP-319.

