3.8.2 Dose Modification and Discontinuation

The actions in Table 3-1 should be taken for any Grade 4 toxicity or unmanageable Grade 3 toxicity. In addition, the actions in Table 3-1 should be taken when modification of the acalabrutinib dose is recommended for specific treatment-related AEs as listed in Table 3-2.

Table 3-1. Dose Modification Actions for Acalabrutinib

| Occurrence | Action |
|------------|---------------------------------------------------------------------------|
| 1st - 2nd | Hold acalabrutinib until recovery to Grade ≤1 or baseline; may restart at |
| | original dose level (100 mg BID) |
| 3rd | Hold acalabrutinib until recovery to Grade ≤1 or baseline; restart at |
| | 100 mg QD |
| 4th | Discontinue acalabrutinib |
| | |

Abbreviations: BID = twice daily; QD = once daily.

Dependent on the subject's initial dose level, subjects who cannot tolerate a rechallenge at the lowest recommended dosages of acalabrutinib and/or ACP-319 should be removed from study treatment.

Protocol: ACE-LY-001

If acalabrutinib and/or ACP-319 are reduced for apparent treatment-related toxicity, the doses need not be re-escalated, even if there is minimal or no toxicity with the reduced doses. However, if the subject tolerates a reduced dose of acalabrutinib and/or ACP-319 for ≥4 weeks then the dose may be increased to the next higher dose level at the discretion of the investigator and after discussion with the medical monitor. Such reescalation may be particularly warranted if further evaluation reveals that the AE that led to the dose reduction was not treatment related.

ACP-319 should be held in subjects with evidence of CMV infection of any grade or viremia (positive PCR or antigen test). ACP-319 may be restarted once the subject is PCR negative, as per investigator discretion. If ACP-319 is resumed, monitor (by PCR or antigen test) for CMV reactivation at least monthly and consider administering pre-emptive CMV therapy. Refer to Section 4.1.24 for monthly CMV testing.

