4.0 STUDY ACTIVITIES AND ASSESSMENTS

The schedule of events is provided in Appendix 5. Descriptions of the scheduled evaluations are outlined below and complete information on study drug and dosing is provided in Section 3.5.

Before study entry, throughout the study, and at the follow-up evaluation, various clinical and diagnostic laboratory evaluations are required. The purpose of obtaining these detailed measurements is to ensure adequate safety and tolerability assessments. Clinical evaluations and laboratory studies may be repeated more frequently if clinically indicated.

Protocol: ACE-LY-001

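### Section 3.5, the protocol's named dosing section, still lists ACP-319 combination regimens and lacks the Amendment 6 monotherapy note found in Section 3.0 and the synopsis

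*Protocol*

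**What the plan says.** Section 3.0 of the protocol states for Part 1, for Part 2 and again under the study schema: "Under Amendment 6 of this protocol, all active subjects will receive acalabrutinib monotherapy (100 mg BID"). The synopsis says the same. It also records that under Amendment 5 subjects on the combination stopped ACP-319 and went on with acalabrutinib alone.

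Section 3.5 (Study Drug Dosing) lists three Part 1 cohorts, each combining acalabrutinib with ACP-319, and then gives Part 2 as "Acalabrutinib 100 mg BID and ACP-319 50 mg BID continuously". The only qualification, printed once for each part, is "Note: Under Amendment 3 of this protocol, subjects with CLL/SLL will receive acalabrutinib monotherapy (100 mg BID"). Amendment 6 is not mentioned there.

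Section 4.0 tells the reader that "complete information on study drug and dosing is provided in Section 3.5". Section 3.12, on withdrawal for progression, refers to Sections 3.5 and 3.8 for the dose level the protocol allows.

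The dose-modification text still covers ACP-319. Section 3.8 says that, if both drugs were withheld, acalabrutinib "should be given alone for at least 7 days, and the subject monitored closely for recurrence of AEs, before adding ACP-319". Section 3.8.2 says of CMV infection that "ACP-319 may be restarted once the subject is PCR negative, as per investigator discretion". Table 3-2 keeps an ACP-319 column with instructions for resuming the drug.

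**The concern.** A dosing section should give one answer to the question of what an active subject takes today. Read alone, Section 3.5 gives the combination to everyone except CLL/SLL subjects, while Section 3.0 gives acalabrutinib alone to everyone. Both are current text, so the conflict does not come from comparing the protocol with its amendment log.

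What is at stake is subject safety. Section 3.9.2 reports hepatitis with the combination. The rest of this version is built around acalabrutinib alone: the risk section and the reference safety information cover acalabrutinib only, and the single schedule of assessments (Appendix 5) has no CMV row, although Section 4.1.24 requires monthly CMV testing in anyone receiving ACP-319. A site that gave or re-added ACP-319 on the strength of Section 3.5 or 3.8 would have no matching schedule to follow.

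**Working it through.** No power, error rate or sample size is involved. The check sets the passages side by side and then works out the size of the disagreement.

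**Step 1: the same regimen list in two places.** The synopsis prints the Part 1 and Part 2 regimens as Section 3.5 does, but puts the override directly after the Part 2 line: "ACP-319 50 mg BID continuously Note: Under Amendment 6 of this protocol, all active subjects will receive acalabrutinib monotherapy (100 mg BID"). In Section 3.5 the line stands without it. The document therefore has a way of marking the combination as superseded, and did not use it in Section 3.5.

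**Step 2: is Section 3.5 operative?** Section 4.0 names it for complete dosing information and Section 3.12 depends on it. Nothing in it is marked as history. Sections 3.0 and 3.4.3, by contrast, add in places that ACP-319 was given previously.

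**Step 3: who is affected?** For CLL/SLL subjects the Amendment 3 note in Section 3.5 already gives acalabrutinib alone at 100 mg BID, so the sections agree. The conflict is confined to active subjects with other histologies.

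**Step 4: size of the conflict.** Daily ACP-319 = 2 × the BID dose in Section 3.5. Under the Amendment 6 note it is 0.

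| Group in Section 3.5 | ACP-319 BID dose | Section 3.5, per day | Section 3.0, per day | Difference |
|---|---|---|---|---|
| Part 1 Cohort 1 | 25 mg | 2 × 25 = 50 mg | 0 | 50 mg |
| Part 1 Cohort 2 | 50 mg | 2 × 50 = 100 mg | 0 | 100 mg |
| Part 1 Cohort 3 | 100 mg | 2 × 100 = 200 mg | 0 | 200 mg |
| Part 2 | 50 mg | 2 × 50 = 100 mg | 0 | 100 mg |

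The acalabrutinib dose is 100 mg BID in both sections, so they differ on ACP-319 only.

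**Step 5: what the restart text requires.** The Section 3.8 rule applies only if both drugs were withheld. The Section 3.8.2 rule permits a restart and does not require one. Section 3.9 describes Table 3-2 as guidance open to investigator judgment. These passages presuppose that ACP-319 is in use and do not order it. They are unmarked leftovers, and the direct contradiction lies in Section 3.5.

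**The case against.** The strongest reply is that the regimen for active subjects is settled many times over. The Amendment 6 note appears repeatedly in the synopsis and Section 3.0, and the Amendment 5 statement says that ACP-319 was stopped. Appendix 5 dispenses acalabrutinib only, and its first footnote applies it to subjects who have been off ACP-319 for at least 3 cycles. Table 3-1 covers acalabrutinib alone. On this view Section 3.5, with its sequential cohorts and Cycle 1 DLT rules, is plainly retained history. Most of this stands: the intent is fairly clear, and a site would have to overlook a good deal of text to give ACP-319. It does not remove the conflict, because the section named for dosing is the one without the note.

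A reader might also infer two stronger things that the documents do not support. The first is that Sections 3.8 and 3.8.2 direct combination dosing; their wording is conditional or permissive. The second is that safety data after the switch could not be read as monotherapy data. Dosing changes must be entered on the eCRF (Section 3.8.2). Section 7.7 has the lots of each drug dispensed to a subject logged, with date and quantity. Section 5.4.3 describes relative dose intensity for both drugs, and Section 5.4.1 summarises AEs by relationship to each. Any ACP-319 exposure should be visible in these records, and nothing in the protocol indicates that any occurred after the switch.

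**Conclusion.** The point holds as an inconsistency in operative dosing text. It is not a flaw in the design or the analysis. It rests on reading Section 3.5 as current, which its lack of any historical label and the references from Sections 4.0 and 3.12 support. The protocol does not give the number of active subjects outside CLL/SLL, so the number affected is unknown. The likelihood of a dosing error is modest, given how often the Amendment 6 note is repeated elsewhere. The point is still worth correcting because a wrong reading bears on subject safety. No view is taken here on which regimen or restart rule is right.

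**What to change.** The sponsor should reconcile Sections 3.5, 3.8, 3.8.2 and Table 3-2 with Section 3.0, so that one regimen statement applies to active subjects. Section 3.5 should state the regimen that the sponsor confirms as in force under Amendment 6. Each remaining ACP-319 instruction should be labelled as current or historical. Until the text is corrected, sites should be told in writing which passage governs.

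The cost is a text edit and a site memo. Sample size, endpoints and analyses are unaffected.
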